6.2.3 Percent Change in the Average Number of Seizures per Cluster from Baseline

Post-baseline number of seizures per cluster will be calculated as total number of cluster seizures divided by total number of clusters during the 26-week open-label treatment period. Baseline number of seizures per cluster will be calculated as total number of cluster seizures divided by total number of clusters during the baseline period. The percent change in the number of seizures per cluster from baseline will be calculated as follow for each subject:

$$\left(\frac{(\text{Postbaseline number of seizures per cluster} - \text{Baseline number of seizures per cluster})}{\text{Baseline number of seizures per cluster}} \right) \times 100\%$$

Summary statistics for baseline and post-baseline values and the arithmetic and percent changes will be presented by cohort separately using descriptive statistics. A subject data listing will be provided.

6.2.4 Percent Change in Total Seizure Frequency (Individual Seizures and Clusters) per 28-day Period from Baseline per Seizure Subtype

This endpoint is the same as the primary efficacy endpoint, except that the frequencies are calculated for each seizure subtype separately.

Summary statistics for baseline and post-baseline values and the arithmetic and percent changes will be presented by cohort separately using descriptive statistics for each seizure subtype that has more than 5 subjects with positive baseline seizure count. A subject data listing will be provided.

6.2.5 Change in the Percentage of Individual Seizure and Cluster Free Days from Baseline

Post-baseline percentage of individual seizure and cluster free days will be calculated as the number of days in the 26-week open-label treatment period free of both individual seizures and clusters divided by the number of days with available individual seizure or cluster occurrence data in the period and multiplied by 100. Baseline percentage of individual seizure and cluster free days will be calculated as the number of days in the baseline period free of both individual seizures and clusters divided by the number of days with available individual seizure or cluster data in the baseline period, multiplied by 100.

Baseline and post-baseline values and arithmetic changes from baseline in seizure and cluster free days will be summarized by cohort separately using descriptive statistics. A subject data listing will be provided.

6.2.6 Change in the Percentage of Individual Seizure Free Days from Baseline

Post-baseline percentage of individual seizure free days will be calculated as the number of individual seizure free days in the 26-week open-label treatment period divided by the number of days with available individual seizure occurrence data in the period and multiplied by 100.

Baseline percentage of individual seizure free days will be calculated as the number of individual seizure free days in the baseline period divided by the number of days with available individual seizure or cluster data in the baseline period, multiplied by 100.

Baseline and post-baseline values and arithmetic changes from baseline in seizure free days will be summarized by cohort separately using descriptive statistics. A subject data listing will be provided.

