6.2.2 Percent Change in Cluster Frequency per 28-day Period from Baseline

Post-baseline 28-day cluster frequency will be calculated as the total number of clusters in the 26-week open-label treatment period divided by the number of days with available cluster count data in the period, multiplied by 28. Baseline 28-day cluster frequency will be calculated as the total number of clusters in the baseline period divided by the number of days with available cluster count data in the period, multiplied by 28. The percent change from baseline in 28-day cluster frequency will be calculated as (post-baseline 28-day cluster frequency minus baseline 28-day seizure frequency) divided by baseline 28-day cluster frequency, multiplied by 100%. (If on a given day seizure data are available then if no cluster data are available the cluster count for that day will be considered as zero. This is done since parents/caregivers often did not record the cluster information if there were no seizures.)

Summary statistics for the baseline and post-baseline values and the arithmetic and percent changes will be presented by cohort separately using descriptive statistics. A subject data listing will be provided.

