6.2.7 Change in the Percentage of Cluster Free Days from Baseline

Post-baseline percentage of cluster free days will be calculated as the number of cluster free days in the 26-week open-label treatment period divided by the number of days with available cluster occurrence data in the period and multiplied by 100. Baseline percentage of cluster free days will

be calculated as the number of cluster free days in the baseline period divided by the number of days with available individual seizure or cluster data in the baseline period, multiplied by 100.

On days where sites recorded individual seizure data, some recorded cluster data only when there were clusters; hence days for which individual seizure data are available and no cluster data are available will be considered as cluster free days.

Baseline and post-baseline values and arithmetic changes from baseline in cluster free days will be summarized using descriptive statistics by cohort. A subject data listing will be provided.

6.2.8 Change in the Longest Period of Time Individual Seizure and Cluster Free (%) from Baseline

The post-baseline longest period of time seizure/cluster-free is defined as the longest individual seizure and cluster free period (days) in the 26-week open-label treatment period divided by the number of days with available individual seizure or cluster occurrence data during the 26-week open-label treatment period, and then multiplied by 100%. The baseline longest period of time seizure/cluster-free is defined as the longest individual seizure and cluster free period (days) in the baseline period divided by the number of days with available individual seizure or cluster data during the baseline period, and then multiplied by 100%. For both periods, the longest period is based on the number of days without an interruption of a day with an individual seizure or cluster. If there is an interruption of a day without seizure or cluster data, then that day will not count. For example, if there are seizures on January 1st, no seizures or clusters on January 2nd thru 4th, no seizure or cluster data on January 5th, no seizures or clusters on January 6th, and there are seizures on January 7th, then the longest period of time seizure/cluster free in this interval would be 4 days (January 2nd thru 4th and January 6th).

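### SAP 6.2.6 uses a different denominator at baseline and post-baseline and needs one rule; 6.2.7 has the same mismatch in wording but needs only a clarifying clause

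*SAP*

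**What the plan says.** SAP 6.2.6 (individual seizure free days) gives two denominators. At baseline the percentage is the "number of individual seizure free days in the baseline period divided by the number of days with available individual seizure or cluster data". Post-baseline, the free days are "divided by the number of days with available individual seizure occurrence data in the period and multiplied by 100".

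SAP 6.2.7 (cluster free days) follows the same pattern. At baseline it is the "number of cluster free days in the baseline period divided by the number of days with available individual seizure or cluster data"; post-baseline, the free days are "divided by the number of days with available cluster occurrence data in the period and multiplied by 100". It adds a rule that is not limited to one period: "days for which individual seizure data are available and no cluster data are available will be considered as cluster free days". The reason given is that, among sites recording individual seizures, "some recorded cluster data only when there were clusters".

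The neighbouring sections each keep one rule for both periods. 6.2.2 (cluster frequency) uses days with cluster counts in both, "divided by the number of days with available cluster count data in the period, multiplied by 28", and provides that where seizure data exist, "if no cluster data are available the cluster count for that day will be considered as zero". 6.2.5 and 6.2.8 use days with either kind of data in both periods.

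SAP 2.5 rules out imputation unless otherwise specified. Neither document says how a day with a cluster entry but no individual seizure entry counts in 6.2.6.

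**The concern.** Both endpoints are arithmetic changes from baseline in an uncontrolled study. A denominator that differs between the periods can produce a change that is not in the child, and there is no control arm in which the same artefact would appear and cancel. Cohorts were planned at up to 10 subjects, so a few affected diaries could move a cohort summary. Two programmers working from the text could also code different derivations.

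No reason is given for a period-specific rule. The baseline denominators of 6.2.6 and 6.2.7 read the same as the one in 6.2.5, which suggests carried-over text rather than a choice; that is an inference. The two endpoints are items 6 and 7 of the eleven secondary endpoints in SAP 1.2.2, and the months 1-3 analysis in 6.3 inherits their wording.

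**Working it through.** The plan states no figure on this point, so there is nothing to reproduce. The check asks what each wording gives for a child whose true pattern is the same in both periods. All shares and day counts below are assumptions; the documents give none.

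**6.2.6.** Let q be the share of days with individual seizure data that are free of individual seizures, and s the share of available days with cluster data only. Three readings are open:

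- A. Cluster-only days are never counted as free. Baseline q(1-s); post-baseline q; change q·s.
- B. They are counted as free at baseline and left out of both terms post-baseline. Baseline q(1-s)+s; post-baseline q; change -s(1-q).
- C. They are counted as free in both numerators, with the same s in both periods. Baseline q(1-s)+s; post-baseline [q(1-s)+s]/(1-s).

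With q = 60%:

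| s | A | B | C |
|---|---|---|---|
| 0% | 60.0 to 60.0 (0) | 60.0 to 60.0 (0) | 60.0 to 60.0 (0) |
| 2% | 58.8 to 60.0 (+1.2) | 60.8 to 60.0 (-0.8) | 60.8 to 62.0 (+1.2) |
| 5% | 57.0 to 60.0 (+3.0) | 62.0 to 60.0 (-2.0) | 62.0 to 65.3 (+3.3) |
| 10% | 54.0 to 60.0 (+6.0) | 64.0 to 60.0 (-4.0) | 64.0 to 71.1 (+7.1) |

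Over q = 30% to 70% and s = 0% to 20%, A runs from 0 to +14.0 points, B from 0 to -14.0, and C from 0 to +19.0.

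**Effect of aligning 6.2.6.** Assumed counts: baseline 84 days, 8 of them cluster-only, 38 free; post-baseline 182 days, 18 cluster-only, 82 free; cluster-only days not counted as free.

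- As worded: 38/84 = 45.2% to 82/(182-18) = 82/164 = 50.0%, +4.8 points.
- Individual-data days in both periods: 38/76 = 50.0% to 82/164 = 50.0%, 0 points.
- Either kind of data in both periods: 38/84 = 45.2% to 82/182 = 45.1%, -0.2 points. The residue arises because the cluster-only shares differ slightly (8/84 = 9.5%, 18/182 = 9.9%).

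**6.2.7.** Let N be days with either kind of data, c days with a cluster, and f days with the cluster field filled in. The baseline percentage is (N-c)/N. The blank-day rule puts the N-f blank days in the numerator as cluster free.

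- Literal post-baseline denominator: (N-c)/f, which exceeds 100% whenever N-f > c, that is, when blank days outnumber cluster days. With N = 100, c = 10 and 25 blank days: 90/75 = 120%. This reading cannot be meant.
- Blank days treated as available: the denominator is f + (N-f) = N, so the percentage is (N-c)/N, as at baseline. The artefact is 0 for any f and c.

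**The case against.** The strongest reply on 6.2.6 is that the effect is hypothetical. It needs days with a cluster entry and no individual seizure entry, and the only gap the SAP describes runs the other way: seizure data present, cluster field blank. With no cluster-only days the two denominators are identical. This stands, and it is why no bias is asserted. It does not repair the text, because the SAP treats the two kinds of data as separately available and its baseline denominator expressly admits days with either.

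On 6.2.7, the reply is that blank cluster fields are already dealt with. This largely stands. A reader might infer that the SAP has no rule for them, or that cluster free days are understated post-baseline because blank days drop out. The documents do not support either inference: 6.2.7 counts those days as cluster free, and 6.2.2 gives the matching zero count. Dropping them from both terms would contradict 6.2.7. What remains is that 6.2.7 states the rule for the numerator and leaves the denominator to be inferred.

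A third reply is that any single rule would do for 6.2.6, including days with either kind of data as in 6.2.5 and 6.2.8. This also stands; the choice below is a preference with a modest reason.

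Finally, SAP 2.1 provides subject listings of source data and derived efficacy variables, so a mismatch could be found and re-derived. That limits the harm, but stating the rule is cheaper.

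**Conclusion.** The inconsistency in wording is certain in both sections. For 6.2.6 it is a real gap whose effect on any reported value is unknown: zero without cluster-only days, and otherwise of a sign and size that depend on an unstated classification (+6.0, -4.0 or +7.1 points at an assumed q = 60% and s = 10%). For 6.2.7 it is a matter of wording; on the coherent reading the periods match, and no artefact size is claimed.

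A reader might infer that the plan tilts these endpoints towards benefit. The documents do not support that: they report no cluster-only days, and the sign reverses with the classification. Nor do they show that the PCDH19 results are wrong, since they do not say how those values were derived.

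The point is minor. It is confined to two descriptive secondary endpoints and their months 1-3 repeat. The primary endpoint, 6.2.5 and 6.2.8 are unaffected, and of the free-day measures SAP 9 lists only the combined one for the extension.

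**What to change.** - **6.2.6:** use one denominator in both periods. The simplest is days with individual seizure data, as already written post-baseline, with cluster-only days left out of numerator and denominator in both. Days with either kind of data in both periods, with the class of cluster-only days stated, would also remove the mismatch. The first option has the advantage that a shift in the share of cluster-only days between periods does not by itself move the percentage.
- **6.2.7:** word the post-baseline denominator as at baseline (days with either kind of data), so that days treated as cluster free are plainly in it.
- **6.3:** apply both changes to the months 1-3 repeat.
- **PCDH19 cohort:** SAP 11 says it was analysed on completion of the 26-week period. Check which denominators were used, and re-derive with disclosure if they were mismatched.

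The cost is two or three sentences in the SAP, the matching derivations, and the PCDH19 check. A count of cluster-only days by period would show at once whether 6.2.6 matters in practice.

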6.2.7 Change in the Percentage of Cluster Free Days from Baseline

Post-baseline percentage of cluster free days will be calculated as the number of cluster free days in the 26-week open-label treatment period divided by the number of days with available cluster occurrence data in the period and multiplied by 100. Baseline percentage of cluster free days will

be calculated as the number of cluster free days in the baseline period divided by the number of days with available individual seizure or cluster data in the baseline period, multiplied by 100.

On days where sites recorded individual seizure data, some recorded cluster data only when there were clusters; hence days for which individual seizure data are available and no cluster data are available will be considered as cluster free days.

Baseline and post-baseline values and arithmetic changes from baseline in cluster free days will be summarized using descriptive statistics by cohort. A subject data listing will be provided.

6.2.8 Change in the Longest Period of Time Individual Seizure and Cluster Free (%) from Baseline

The post-baseline longest period of time seizure/cluster-free is defined as the longest individual seizure and cluster free period (days) in the 26-week open-label treatment period divided by the number of days with available individual seizure or cluster occurrence data during the 26-week open-label treatment period, and then multiplied by 100%. The baseline longest period of time seizure/cluster-free is defined as the longest individual seizure and cluster free period (days) in the baseline period divided by the number of days with available individual seizure or cluster data during the baseline period, and then multiplied by 100%. For both periods, the longest period is based on the number of days without an interruption of a day with an individual seizure or cluster. If there is an interruption of a day without seizure or cluster data, then that day will not count. For example, if there are seizures on January 1st, no seizures or clusters on January 2nd thru 4th, no seizure or cluster data on January 5th, no seizures or clusters on January 6th, and there are seizures on January 7th, then the longest period of time seizure/cluster free in this interval would be 4 days (January 2nd thru 4th and January 6th).

Baseline and post-baseline values and arithmetic changes from baseline in the longest period of time seizure or cluster free will be summarized by cohort separately using descriptive statistics. A subject data listing will be provided.

6.2.9 Proportion of Subjects with >= 25%, 50%, or 75% Reduction in 28-day Total Seizure Frequency (Sum of Individual Seizures and Clusters) Compared with Baseline

An R% responder is an individual whose reduction of percent change from baseline to the end of the 26-week open-label treatment period in 28-day total seizure frequency is greater than or equal to R%. R% will be 25%, 50%, and 75%. Frequency of seizures is based on the sum of the individual seizures and the clusters.

The number and percentage of responders will be summarized by cohort. In addition, for the main 26-week open-label treatment period of the study, a cumulative responder curve figure will be provided, in which the X-axis represents amount of improvement in increments of 5%, and the Y-axis represents the percentage of subjects improving by at least the amount on the X-axis. The cohorts will be presented separately within the figure. A subject data listing will be provided.

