9.5 Efficacy and Safety Variables

9.5.1 Calculation of Baseline

Baseline will be calculated from a maximum of 12 weeks' of seizure calendar data with a minimum of 4 weeks of data required, which should include contiguous retrospective ratings provided after signing informed consent. Acceptable retrospective daily seizure

data include a diary record of the frequency and type of seizures by day. Source data may include a seizure diary or calendar, recorded data from smart phones or other devices. Seizure clusters are to be identified, and the number of seizures in the daily cluster should be counted or given as best estimate.

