1. INTRODUCTION

The purpose of this statistical analysis plan (SAP) is to describe the procedures and the statistical methods that will be used to analyze and report results for Protocol 1042-0900 (Amendment 8.1, August 28, 2017).

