2.2.2 Modified Intention-To-Treat Population (MITT)

The MITT population includes all subjects who entered into the study and received at least 1 dose of study drug and provided at least 1 day of post-baseline seizure calendar data. This is the primary population for the efficacy analyses.

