6. EFFICACY ANALYSES

All efficacy analyses will be summarized by cohort in the MITT population. These summaries will include only the CDKL5, LGS, and PCDH19 cohorts since only 2 patients were enrolled in the CWS cohort. However, the CWS cohort will be included in the subject data listings. For the analyses of seizures and clusters, the baseline period consists of up to 12 weeks before the first day of treatment, and the 26-week open-label treatment period starts with the day following the first day of treatment until the final visit for subjects who do not enter the OLE and up to the day before the first dose of OLE treatment for those who do. The first day of treatment is not in either period since the times of seizures were not collected.

Seizure diary compliance will be summarized by cohort. The calculated compliance is:
 $100 \times (\text{Number of Days with Available Seizure or Cluster Diary}) / (\text{Last Available Seizure or Cluster Diary Date} - \text{First Available Seizure or Cluster Diary Date} + 1)$.

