6.2.10 CGII-C and CGII-P

Clinical Global Impression of Improvement –Clinician (CGII-C), or Clinical Global Impression of Improvement –Patient/Caregiver (CGII-P): A 7-point Likert scale completed by the Clinician

or Patient/Caregiver representing the degree to which the subject's epilepsy symptoms have changed relative to baseline. On the CGII-C, 1=very much improved and 7=very much worse.

Frequency and percentage of the responses will be summarized by visit for CGII-C and CGII-P separately. The analysis will be conducted by cohort separately. A subject data listing will be provided.

6.3 ANALYSIS OF MONTHS 1 – 3

In order to explore early signals of efficacy, the seizure and cluster analyses described above will be repeated using just the first 3 months of the post-baseline period, defined as the first 90 days following the first day of treatment (Study Days 2 to 91).

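### SAP 6.2.8 divides the longest seizure-free run by period length, so with no change in seizures completers appear to worsen and subjects with follow-up shorter than baseline appear to improve

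*SAP*

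**What the plan says.** SAP 6.2.8 uses, for the post-baseline value, "the longest individual seizure and cluster free period (days) in the 26-week open-label treatment period divided by the number of days with available" seizure or cluster data in that period, times 100. For baseline it uses "the longest individual seizure and cluster free period (days) in the baseline period divided by the number of days with available individual seizure or" [...], that is, the same ratio over the baseline days that have any diary record, times 100. A day with a seizure or cluster ends a run; a day without diary data is skipped. The summary is made within cohort: "Baseline and post-baseline values and arithmetic changes from baseline in the longest period of time seizure or cluster free will be summarized".

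The lengths of the two periods come from elsewhere:
- SAP 6: "the baseline period consists of up to 12 weeks before the first day of treatment". Treatment runs for 26 weeks, starting the day after the first dose.
- Protocol 9.5.1: "Baseline will be calculated from a maximum of 12 weeks' of seizure calendar data with a minimum of 4 weeks of data required". This is the supplied protocol. The SAP cites the later Amendment 8.1, which was not available, so the actual baseline lengths are unknown.
- SAP 2.2.2: the efficacy population needs only subjects who "provided at least 1 day of post-baseline seizure calendar data". SAP 2.5 imputes nothing unless otherwise specified.
- SAP 6.3: the seizure and cluster analyses are "repeated using just the first 3 months of the post-baseline period, defined as the first 90 days following the first day of treatment", in addition to the 26-week analysis.

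Neither document matches the period lengths, sets a minimum follow-up for this endpoint or adjusts for length.

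**The concern.** Dividing by days with data works for a count of seizure-free days, which grows in proportion to the time observed. It does not work for a maximum. Lengthening the window from 28 to 182 days multiplies the denominator by 6.5, while the longest run may only double. The percentage therefore falls as the window lengthens, even when the child's seizures have not changed.

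A reader will take zero as no effect, a fall as worsening and a rise as benefit. If the no-effect value is negative for completers and positive for anyone followed for less time than their own baseline, a fall cannot be read as harm, and a rise in a subject with short follow-up cannot be read as benefit. With about 10 subjects planned per cohort, a few short baselines or early discontinuations can move a cohort mean.

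**Working it through.** **The SAP's own example.** Seizures on 1 January, free on 2 to 4 January (3 days), no data on 5 January (skipped), free on 6 January (1 day), seizures on 7 January. Longest run = 3 + 1 = 4 days, as the SAP states. The run rule is clear; the problem is the denominator.

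**Direction without a probability model.** One seizure every 7 days throughout gives a longest run of 6 days in any period: 6/28 = 21.4%, 6/84 = 7.1%, 6/181 = 3.3%.

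**Inputs for the size.**
- Baseline of 28, 56 or 84 days (protocol 9.5.1 minimum, an intermediate value, SAP 6 maximum).
- Completer: 182 days. Excluding the first dosing day makes it 181, which moves the results below by at most about 0.2 points.
- Assumption: independent days, constant probability p of a seizure day. The range is 1/42 (one cluster per 6 weeks, inclusion criterion 4a) to 0.5. The main example is p = 4/28, the minimum in criterion 4b with each seizure on its own day.

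**Formula.** Let v(r) be the probability that the current free run is r days and no run so far has exceeded k days. Each day, new v(0) = p × Σ v(r), and new v(r+1) = (1 - p) × v(r) for r < k. After n days P(L ≤ k) = Σ v(r), and E[L] = Σ over k from 0 to n - 1 of [1 - P(L ≤ k)]. Expected change = 100 × (E[L post]/n post - E[L base]/n base).

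**Expected longest run at p = 4/28.**

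| Days with data | E[L], days | Percent of days |
|---|---|---|
| 14 | 8.40 | 60.0 |
| 28 | 12.48 | 44.6 |
| 42 | 15.02 | 35.8 |
| 56 | 16.85 | 30.1 |
| 84 | 19.44 | 23.1 |
| 90 | 19.88 | 22.1 |
| 182 | 24.42 | 13.4 |

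For a completer with no effect, 13.4 - 44.6 = -31.2, 13.4 - 30.1 = -16.7 and 13.4 - 23.1 = -9.7. With seizure days halved, the expected run over 182 days is about 42 days (23.1%), so the change is 23.1 - 44.6 = -21.5 for a 28-day baseline.

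**Expected change in percentage points, by baseline length** (from unrounded values).

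| Scenario | 28 days | 56 days | 84 days |
|---|---|---|---|
| No effect, 182 days, p = 4/28 | -31.2 | -16.7 | -9.7 |
| Share of these subjects strictly worse | 99% | 96% | 88% |
| No effect, 182 days, p from 1/42 to 0.5 | -42 to -11 | -28 to -5 | -19 to -3 |
| No effect, 182 days, p = 0.9 | -3.2 | -1.5 | -0.8 |
| Halved, 182 days, p = 4/28 | -21.5 | -7.0 | -0.1 |
| Halved, 182 days, p from 1/42 to 0.5 | -26 to -7 | -11 to -1 | -1.4 to +1.3 |
| Halved, 182 days, p = 0.9 | 0.0 | +1.7 | +2.4 |
| Quartered, 182 days, p = 0.2 | -6.0 | +6.4 | +12.0 |
| No effect, 14 days, p = 4/28 | +15.4 | +29.9 | +36.9 |
| No effect, 42 days, p = 4/28 | -8.8 | +5.7 | +12.6 |
| No effect, SAP 6.3 repeat (90 days), p = 4/28 | -22.5 | -8.0 | -1.1 |

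**Sensitivity to the model.** With a Poisson rate of 4 per 28 days and 181 treatment days, the no-effect change is -32.2 (28-day baseline) and -10.2 (84-day baseline); with 14 days of follow-up it is +15.4 and +37.5. With serially correlated days (lag-1 correlation 0.3, p = 4/28), a completer with no effect shows -35.4, -20.1 and -11.9 for the three baselines.

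**The case against.** The direction is not in dispute. The case for leaving the endpoint alone rests on scope and cost.

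- **Size depends on unknowns.** The largest figures need a 4-week baseline, and that minimum comes from an earlier protocol than the one the SAP cites. Entry criteria set only a minimum seizure frequency; at p = 0.9 the no-effect fall is 3.2 points or less, and there is none for subjects with seizures every day or none in either period. This stands as a limit on size. The fall still occurs at every baseline length in the range and at every density strictly between never and daily.
- **SAP 6.3 already helps.** For a 12-week baseline the 90-day repeat leaves only -1.1. It leaves -22.5 and -8.0 for 4 and 8 weeks, and it does not replace the 26-week result.
- **The endpoint is minor.** It is descriptive, and both period values and a subject listing are planned. That stands and limits the consequence. A descriptive change is nevertheless read against zero.
- **The repair has its own limits.** An average of window maxima, capped at the window length, is no longer the longest free period on treatment. Under a real effect it still depends on window length: halving at p = 1/42 gives +7.3, +11.5 and +14.1 points for 28-, 56- and 84-day windows. With a single follow-up day it reduces to the percentage of free days, as in SAP 6.2.5. SAP 11 also says the PCDH19 cohort has already been analysed, so redefinition would be post hoc for that cohort. All of this stands and calls for disclosure, but none of it makes the current comparison valid.

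**Conclusion.** The endpoint is wrong as written and should be corrected. Its expected value under no effect is not zero and depends on each subject's baseline and follow-up length. At p = 4/28 it is -31.2 to -9.7 points for completers and +15.4 to +36.9 with 14 days of follow-up, across 28- to 84-day baselines. The sign turns where days with data on treatment fall below that subject's own baseline days. Halving seizure days reads as worsening with 4- to 8-week baselines at low to moderate seizure density, and as about zero with 12 weeks.

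The sizes assume independent days at a constant rate and an assumed range of baseline lengths; the direction does not rest on the independence assumption. A clear rise in a completer remains informative. The primary endpoint, a rate, is unaffected, and the percentage of seizure- and cluster-free days in SAP 6.2.5 does not have this length dependence.

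**What to change.** Give each subject windows with the same number of diary days in both periods.

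1. Split treatment into consecutive windows of that subject's baseline diary length and drop leftover days at the end: 182 = 6 × 28 + 14 = 3 × 56 + 14 = 2 × 84 + 14.
2. Take the longest free run in each window, average over windows, and report the change as a percentage of the common window length. Put days in the listing.
3. If post-baseline data are shorter than baseline, cut the baseline into windows of the post-baseline length, and flag very short follow-up.
4. Do not impose a 28-day window on everyone. At one cluster per 6 weeks, (41/42)^28 = 51% of such windows are entirely free, and halving the rate adds only about 2 days.
5. State in SAP 11 that the definition changed after the PCDH19 analysis. The existing measure can be kept in days, with both denominators, as a description.

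In simulation at p = 1/42, 4/28, 0.2 and 0.5, the no-effect mean was within 0.3 points of zero for both 182 and 14 post-baseline days. At p = 4/28, halving seizure days lengthens the expected run by 5.17, 9.42 and 12.19 days in 28-, 56- and 84-day windows: 5.17/28 = +18.5, 9.42/56 = +16.8 and 12.19/84 = +14.5 points.

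The cost is SAP wording, a short program change on the same diary data, and the disclosure. Runs that cross a window boundary are cut, leftover days are unused, short windows are noisier, and subjects with a 4-week baseline and infrequent clusters still meet a ceiling. Because effect size varies with window length, show baseline length beside each subject's result. A footnote alone would be cheaper, but it would leave a change whose no-effect value is not zero.
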